7.3.1.3. PROMIS Short Form – Sleep-Related Impairment (8a)

The PROMIS Short Form – Sleep-Related Impairment (8a) is an 8-item questionnaire. Each item on the measure is rated on a 5-point scale (1 = Not at all; 2 = A little bit; 3 = Somewhat; 4 = Quite a bit; and 5 = Very much) with a range in score from 8 to 40 with higher scores indicating greater severity of sleep-related impairment. The recall period will be the past 24 hours for the VC period and the past 7 days for the LTS period. The raw scores on the 8 items should be summed to obtain a total raw score. If 4 or more of the total items on the measure are missing, the scores should not be used.

For total raw score, the baseline will be determined by averaging the 7 daily scores before Day 1 (Day -7 to Day -1). The by-visit score for post-baseline VC visits will be determined by averaging the 7 daily scores before the visit day. If 4 or more daily scores are missing (out of the 7), the by-visit score at the visit will be set to missing.

Clinical meaningful difference is defined as a \geq 6-point change over baseline. The total raw score will be summarized by visit and by treatment. The proportion of participants with a \geq 6-point (clinically meaningful) improvement in the PROMIS Short Form – Sleep-Related Impairment (8a – 24-hour recall) score will be summarized by treatment group for participants with baseline \geq 6.

7.3.2. Key Secondary Efficacy Analysis

Key secondary efficacy analyses will be conducted in the ITT population in the VC period. If the primary objective is achieved, the statistical comparisons for key secondary endpoints will be tested with the procedures specified in [Figure 2](#). All of the key secondary endpoints will be analyzed using the similar logistic regression models as specified in the primary efficacy analysis.

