10. STATISTICS

10.1. Sample Size Determination

Approximately 600 participants will be randomized 2:2:1 to ruxolitinib 0.75% BID, 1.5% BID, or vehicle and stratified by baseline IGA (2, 3) and region (North America or other). The sample size calculation is based on the Fisher exact test for the statistical comparison on the primary efficacy endpoint. The Fisher exact test is used to provide a conservative evaluation of statistical power, and it is accurate when there is a small expected number of responders in the vehicle group. Based on the results from a Phase 2, randomized, dose-ranging study (INCB 18424-206), the IGA-TS at Week 8 is assumed to be 45% and 30% for active arms (1.5% BID and 0.75% BID, respectively) versus 10% for placebo. Using a 2-sided alpha of 0.025, the sample size will have > 95% power to detect a difference between each of the 2 active treatment groups versus vehicle. In addition to provide adequate power for efficacy variables, the sample size is determined to provide an adequate database for safety evaluation.

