7.2.2. Primary Efficacy Analyses

The primary analysis will be based on the ITT population in the VC period. The primary alternative hypothesis (superiority of ruxolitinib 1.5% BID or 0.75% BID compared with vehicle) will be tested using logistic regression. This model will include the treatment group (1.5% BID, 0.75% BID, and vehicle) and stratification factors (baseline IGA and region). The unadjusted p-values between each treatment group versus vehicle will be calculated based on Wald test, which will be compared with the procedure defined in Section 3.2. Exact logistic regression ([Mehta and Patel 1995](#)) will be used for all of the comparisons if any of the dose levels have an expected cell count less than 5.

Odds ratio and 95% CI in response rates (ruxolitinib cream vs vehicle) at Week 8 will also be computed. All nonresponders in the VC treatment period, as well as all participants who are missing postbaseline values, will be defined as nonresponders for the nonresponder imputation analysis.

The primary outcome will also be examined for PP population using the same model as the primary analysis.

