7.3. Analysis of the Key Secondary Efficacy Parameters

7.3.1. Key Secondary Efficacy Measures

7.3.1.1. Itch Numerical Rating Scale Score

The Itch NRS is a once-per-24 hours ("daily") patient-reported measure of itch intensity assessed using an 11-point scale (0 = no itch to 10 = worst imaginable itch). Participants will be asked to record their highest (worst) level of itch in the evening over the 24-hour recall period.

The Itch NRS score for baseline will be determined by averaging the 7 daily NRS scores before Day 1 (Day -7 to Day -1). The by-visit Itch NRS score for postbaseline visits will be determined by averaging the 7 daily NRS scores before the visit day. If 4 or more daily scores are missing (out of the 7), the Itch NRS score at the visit will be set to missing.

The proportion of participants with a clinically relevant change in itch – defined as a ≥ 4 -point improvement in Itch NRS score from baseline to Week 8 – will be summarized by treatment groups for participants with baseline Itch NRS ≥ 4 .

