7.4.2.3. Categorical Efficacy Endpoints

For the following categorical parameters, summary statistics including sample size, frequency, and percentages will be presented by visits.

- Proportion of participants achieving an IGA of 0 or 1
- Proportion of participants with a \geq 2-point improvement in Itch NRS score
- Proportion of participants with a \geq 3-point improvement in Itch NRS score
- Proportion of participants with a \geq 4-point improvement in Itch NRS score
- Proportion of participants achieving EASI50
- Proportion of participants achieving EASI75

- Proportion of participants achieving EASI90
- Proportion of participants with a \geq 6-point improvement in the PROMIS Short Form (8a) – Sleep-Related Impairment 24-hour recall score
- Proportion of participants with a \geq 6-point improvement in the PROMIS Short Form (8b) – Sleep Disturbance 24-hour recall score
- Proportion of participants with a score of either 1 or 2 of PGIC
- Proportion of participants with a clinically meaningful improvement (\geq 4-point improvement) in DLQI/CDLQI

A logistic regression model with treatment and stratification factors as covariates will be fit at Week 8. The p-values between each ruxolitinib group versus vehicle will be calculated based on Wald test. Exact logistic regression will be used for all of the comparisons if any of the dose levels have an expected cell count less than 5. The NRI will be used to impute postbaseline missing values for binary outcomes based on IGA, EASI, Itch NRS, PROMIS Short Form – Sleep-Related Impairment (8a) scores, PROMIS Short Form – Sleep Disturbance (8b) scores.

For the following categorical endpoints, the number and percentage of participants will be summarized by treatment at each postbaseline visit.

- Proportion of participants in each category of EASI score
- Proportion of participants in each category of IGA score
- Proportion of participants in each category of PGIC score
- Proportion of participants in each category of POEM score
- Proportion of participants in each category of DLQI/CDLQI score
- Proportion of participants in each category of each EQ-5D dimension

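### The alpha-controlled itch and sleep responder tests leave out each endpoint's own baseline score, which costs some power (modest for itch, more for sleep) without affecting validity.

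*SAP*

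**What the plan says.** For the key secondary endpoints, SAP 7.3.2 states: "All of the key secondary endpoints will be analyzed using the similar logistic regression models as specified in the primary efficacy analysis". The model it points to is in SAP 7.2.2: "This model will include the treatment group (1.5% BID, 0.75% BID, and vehicle) and stratification factors (baseline IGA and region"). SAP 7.4.2.3, which lists the same itch and sleep responder variables, repeats the specification: "A logistic regression model with treatment and stratification factors as covariates will be fit at Week 8". No section adds a baseline itch or sleep score to these models. By contrast, SAP 7.4.2.1 plans ANCOVA with the baseline score as a covariate, where applicable, for seven continuous measures, none of them alpha-controlled.

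Six gated hypotheses are affected (SAP 3.2):

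- H13 and H23: itch response, a fall of at least 4 points on a 0 to 10 scale.
- H14 and H24: PROMIS 8b response, a fall of at least 6 points on an 8 to 40 scale.
- H31 and H32: PROMIS 8a response, the same threshold and range.

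Each baseline is a 7-day diary mean, set to missing if four or more days are missing (SAP 7.3.1.1 to 7.3.1.3). Itch response "will be summarized by treatment groups for participants with baseline Itch NRS" of at least 4. Both sleep responses are summarised for participants with a baseline of at least 6.

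**The concern.** A response defined by a fixed number of points depends on where the participant starts. Someone near the floor of the scale has little or no room to fall; someone high on it has plenty. Baseline IGA describes lesion severity and region describes geography, so neither stands in well for baseline itch or sleep. In a logistic model, leaving out a strong baseline predictor lowers the power of the treatment test.

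The tests concerned are links in a fixed sequence. At the 0.025 level, a miss on itch or PROMIS 8b stops that dose's sequence and prevents it from passing alpha to the other dose. PROMIS 8a is tested only if all eight Step 1 hypotheses are rejected. The plan states no power for any itch or sleep test, so nothing in the documents shows that these links have power to spare.

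**Working it through.** **1. The plan's own power figure.** Protocol 10.1 gives the inputs: "Approximately 600 participants will be randomized 2:2:1 to ruxolitinib 0.75% BID, 1.5% BID, or vehicle", so 240, 240 and 120; "The sample size calculation is based on the Fisher exact test"; the Week 8 IGA-TS rate "is assumed to be 45% and 30% for active arms (1.5% BID and 0.75% BID, respectively) versus 10% for placebo"; and "Using a 2-sided alpha of 0.025, the sample size will have > 95% power to detect a difference".

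The normal approximation is power = Φ[(Δ − z·SE0)/SE1], with z = 2.241 for two-sided 0.025, SE0 from the pooled rate and SE1 from the separate rates.

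- 30% v 10%: pooled rate (72 + 12)/360 = 0.2333; SE0 = √(0.2333 × 0.7667 × (1/240 + 1/120)) = 0.0473; SE1 = √(0.21/240 + 0.09/120) = 0.0403; (0.20 − 2.241 × 0.0473)/0.0403 = 2.33; power 99.0%. Full enumeration of the Fisher test gives 98.9%.
- 45% v 10%: more than 99.9% by both methods.

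The stated figure reproduces. It covers IGA-TS only.

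**2. Who can respond at all.**

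- Itch: a 4-point fall needs a baseline of at least 0 + 4 = 4. The itch filter is 4, so everyone it admits can respond. (I take the filter to apply to the gated test; SAP 7.3.1.1 states it for the summary.)
- Sleep: a 6-point fall needs a baseline of at least 8 + 6 = 14. The filter is 6, below the scale minimum of 8, so it removes nobody, and participants at 8 to below 14 stay in although they cannot respond on any arm.

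The documents give no baseline distribution. If sleep baselines are roughly normal with SD 6 (assumed), the share below 14 is Φ((14 − mean)/6): about 31% at mean 17, 16% at mean 20 and 5% at mean 24.

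**3. Effect of adding the baseline score.** The planned three-arm logistic model (Wald test, 0.025, 240/240/120) was simulated 2,000 times per setting, with and without the continuous baseline score. All of the following are assumptions:

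- Baseline itch mean 5, SD 2.4; baseline sleep mean 17, 20 or 24, SD 6.
- Correlation of baseline with Week 8: 0.2 to 0.6 for itch, 0.3 to 0.7 for sleep.
- Mean fall on vehicle: 1.2 for itch, 1.5 for sleep.
- Extra fall on 1.5% and 0.75%: 1.6 and 0.9, or 1.1 and 0.7, for itch; 3 and 2 for sleep.
- 10% missing, counted as nonresponse.

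Effects were set modest so that power is not already near 100%.

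| Setting | Dose | Without score | With score | Gain (points) |
|---|---|---|---|---|
| Itch, corr. 0.4, larger effect | 1.5% | 85.2% | 89.0% | 3.8 |
| Itch, corr. 0.4, larger effect | 0.75% | 31.4% | 34.7% | 3.3 |
| Itch, corr. 0.6, larger effect | 0.75% | 36.4% | 36.8% | 0.4 |
| Itch, corr. 0.2, smaller effect | 1.5% | 41.2% | 46.8% | 5.6 |
| Sleep, mean 20, corr. 0.5 | 1.5% | 75.4% | 83.4% | 8.0 |
| Sleep, mean 17, corr. 0.3 | 1.5% | 48.8% | 64.5% | 15.7 |
| Sleep, mean 17, corr. 0.3 | 0.75% | 22.2% | 33.0% | 10.8 |
| Sleep, mean 20, corr. 0.7 | 1.5% | 92.8% | 94.6% | 1.8 |

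Over all settings the gain was 0.4 to 5.6 points for itch. For sleep it was 1.8 to 15.7 at 1.5% and 4.0 to 10.8 at 0.75%. With no treatment effect, the rejection rate at nominal 2.5% was 1.8 to 2.5% without the score and 1.9 to 2.8% with it.

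**4. How much of the sleep gain is the filter.** In two-arm runs (240 v 120) under similar assumptions, the score added 13.2 points (mean 17, correlation 0.3) and 7.9 points (mean 20, correlation 0.5) with the filter as written. With a filter at 14 it added 5.8 and 4.7. A working filter takes up much of the gain where baselines are low, but not all of it.

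**The case against.** The strongest reply is that nothing is invalid. Adjusting for the randomisation factors alone is a legitimate prespecified choice, applied consistently to the primary and responder endpoints, and Type I error holds either way. That stands: the point concerns efficiency only.

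Three stronger readings might be inferred, and the documents do not support them.

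- **That baseline largely decides who can respond, for itch as well as sleep.** The itch filter already removes those who cannot fall by 4 points, and the remaining gain is small. The description fits sleep, and there part of the cause is the ineffective filter.
- **That a miss at itch is final for that dose and for PROMIS 8a.** Under SAP 3.2, if one dose clears all four of its hypotheses, the other dose's sequence is run at 0.05. A test missed at 0.025 can therefore still be passed, and the gate to PROMIS 8a can still open. The powers above are for single tests at 0.025, not for the whole sequence.
- **That a definite amount of power is lost.** No itch or sleep rates are given. At rates like those assumed for IGA-TS, power is already 98.9% or more and there is almost nothing to gain.

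There are also practical objections. A participant without a 7-day baseline mean would drop out of a covariate model, which conflicts with analysis of the ITT population. Exact logistic regression, required by SAP 7.2.2 when an expected count is below 5, works poorly when conditioned on a continuous mean. The odds ratio becomes conditional on baseline score. All three are fair; the first two can be settled in a sentence each and the third is a matter of reporting. Finally, the word similar in SAP 7.3.2 does not forbid another covariate, but a gated test needs its covariates named in advance and none is named.

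**Conclusion.** The point holds as an efficiency improvement. The six gated itch and sleep tests adjust only for baseline IGA and region, although a prognostic baseline score is available for each. Under the assumed inputs, leaving it out costs roughly 0 to 6 power points for itch and 2 to 16 for sleep. These ranges rest entirely on assumed baseline distributions, correlations, effects and missingness; the documents fix none of them. The direction was the same in every setting run. The sleep figures include the effect of a filter that excludes nobody; correcting it reduces the gain but does not remove it.

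**What to change.** Before unblinding, which SAP 9 places after the primary database lock, amend SAP 7.3.2 as follows:

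- For H13, H23, H14, H24, H31 and H32, add the endpoint's own baseline score (7-day mean Itch NRS, PROMIS 8b or PROMIS 8a) as a continuous covariate next to treatment, baseline IGA and region.
- State how participants with a missing 7-day baseline mean are handled, so that none leaves the model unplanned.
- State that the exact logistic fallback uses the stratification factors only.

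Separately, restate the sleep filter in SAP 7.3.1.2 and 7.3.1.3 so that it selects participants able to improve by 6 points; on an 8 to 40 scale that means a baseline of at least 14. This complements the covariate and does not replace it.

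The cost is SAP wording and programming, with no new data. The downside is that the odds ratio is then conditional on baseline score; crude response rates by arm should still be shown beside it.

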7.4. Analysis of Secondary Efficacy Parameters

7.4.1. Secondary Efficacy Measures

7.4.1.1. SCORing Atopic Dermatitis

SCORAD is a tool to assess the extent and severity (ie, intensity) of eczema and will be completed before, during, and after treatment has begun to determine whether the treatment has been effective. This will be performed during all VC study visits, starting at baseline.

- To determine extent, the rule of 9 or handprint method is used to calculate the eczema affected area (A) as a percentage of the whole body.
- To determine intensity, the intensity of each of the following signs of redness, swelling, oozing/crusting, scratch marks, skin thickening (lichenification), dryness (this is assessed in an area where there is no inflammation) is assessed as follows:
 - None (0)
 - Mild (1)
 - Moderate (2)
 - Severe (3)

Intensity scores are added together to give “B” (maximum score of 18).

- Subjective symptoms, that is, itch and sleeplessness, are scored by the participant using a VAS where “0” is no itch (or no sleeplessness) and “10” is the worst imaginable itch (or sleeplessness).

These scores are added to give “C” (maximum score of 20).

Total score gives approximate weights of 60% to intensity and 20% each to extent and subjective signs (ie, insomnia, etc) for the participant and will be calculated as follows:

Total score = A / 5 + (7 × B) / 2 + C.

7.4.1.2. Time to Itch Response

Time to Itch NRS response is defined as the number of days between the day of randomization and the day of achieving a daily Itch NRS score improvement of at least 2, 3, and 4 points.

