8.2.7.6. Itch Numerical Rating Scale

The Itch NRS is a daily patient-reported measure (24-hour recall) of the worst level of itch intensity. Participants will be asked to rate the itching severity because of their AD by selecting a number from 0 (no itch) to 10 (worst imaginable itch) that best describes their worst level of itching in the past 24 hours as outlined in the SoA (see [Table 3](#)).

Participants will be issued a diary in which to record itch severity. The participants will be instructed to complete the diary each night beginning on the day of screening through the last application of study drug in the VC period. Detailed directions for the administration of an eDiary will be provided in the Study Manual.

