7.4.2. Secondary Efficacy Analysis

All secondary efficacy analyses will be conducted based on the ITT population in the VC and LTS periods.

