7.4.2.4. Time-To-Event Efficacy Endpoints

For the time to achieve Itch NRS score improvement of at least 2, 3, or 4 points, a log-rank test stratified by randomization stratification factors will be used for between treatment group comparisons. The hazard ratio and its 95% CI will be estimated based on the stratified Cox regression model using Efron's method accounting for ties. Kaplan-Meier curves will be presented by treatment groups. The number of participants, number of events and number of censoring will be summarized by treatment groups. The KM estimate of median time will be presented with its 95% CI. The 95% CI will be calculated using the method by Brookmeyer and Crowley (1982).

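### The time-to-itch-response analyses, and the 2- and 3-point responder analyses, set no minimum baseline itch, so they count participants who cannot have the event

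*SAP*

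**What the plan says.** - **Event.** SAP 7.4.1.2 counts days from randomization to "the day of achieving a daily Itch NRS score improvement of at least 2, 3, and 4 points". No minimum baseline is given.
- **Analysis.** SAP 7.4.2.4 states that "a log-rank test stratified by randomization stratification factors will be used for between treatment group comparisons". It adds that "The hazard ratio and its 95% CI will be estimated based on the stratified Cox regression model" and that "The KM estimate of median time will be presented with its 95% CI". No baseline limit appears here either.
- **Population.** SAP 7.4.2: "All secondary efficacy analyses will be conducted based on the ITT population in the VC and LTS periods". Appendix A labels Tables 2.3.6 to 2.3.8 and Figures 4.3.4.1 to 4.3.4.3 as ITT.
- **Scale.** Protocol 8.2.7.6 has the participant rate itch by "selecting a number from 0 (no itch) to 10 (worst imaginable itch").
- **Baseline itch.** SAP 7.3.1.1: "The Itch NRS score for baseline will be determined by averaging the 7 daily NRS scores before Day 1".
- **Existing restriction.** The same section says that the 4-point proportion at Week 8 "will be summarized by treatment groups for participants with baseline Itch NRS" of 4 or more.
- **Responder analyses.** SAP 7.4.2.3 lists the 2-, 3- and 4-point itch proportions with nonresponder imputation and no baseline limit.
- **Entry and strata.** The entry criteria (Protocol 5.1 and 5.2) contain no itch threshold. The strata are baseline IGA and region (SAP 3.1), not itch.

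**The concern.** Improvement cannot exceed the baseline value. A participant who enters with an average itch of 3 can never record a 4-point improvement, whichever arm they are in. The SAP applies this logic to one itch endpoint and does not carry it to the others.

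In a time-to-event analysis these participants sit in every risk set without ever contributing an event. As follow-up proceeds, the more effective arm uses up its possible responders sooner. Its risk set then consists increasingly of people who cannot respond, and the observed hazard ratio drifts toward 1. The Kaplan-Meier cumulative incidence cannot rise above the share able to respond, so the median may not exist even when most of those able to respond do so. In the responder tables both proportions are multiplied by that share, and so is their difference. Stratifying by IGA and region does not separate these participants out.

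What is at stake is the size and reading of secondary estimates: hazard ratios, medians and the 2- and 3-point proportions.

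**Working it through.** **The plan's only power figure.** The documents give no power for itch. Their one figure is more than 95% for IGA-TS (Protocol 10.1, SAP 3.3). With 600 randomized 2:2:1 (240/240/120), two-sided alpha 0.025 and the Fisher exact test, it reproduces: 98.9% for 30% vs 10%, and above 99.9% for 45% vs 10%. It does not bear on this endpoint.

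**Inputs from the documents.** 240 vs 120 participants; an 8-week vehicle-controlled period (56 days); scale floor 0.

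**Assumptions, because the documents are silent.**
- π, the share with baseline below k, is equal in the two arms.
- F₁ and F₀ are the probabilities of having the event by Day 56 among those able to respond (active, vehicle).
- Event times in that group are exponential, with no dropout. Follow-up ends at Day 56, which is inferred from the diary period; the SAP states no censoring rule.
- The calculation is unstratified.

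**Step 1: direction.** Let λⱼ = −ln(1 − Fⱼ)/56 and θ = λ₁/λ₀. Survival in arm j is Sⱼ(t) = π + (1 − π)e^(−λⱼt). The hazard ratio in all randomized participants at time t is

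θ × [π·e^(λ₀t) + (1 − π)] / [π·e^(λ₁t) + (1 − π)].

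For π > 0 and λ₁ > λ₀ the bracketed ratio is below 1 at every t > 0. Example with F₁ = 80%, F₀ = 50% and π = 35%: θ = ln(0.20)/ln(0.50) = 2.32. At Day 56, e^(λ₁t) = 5 and e^(λ₀t) = 2, so the ratio is 2.32 × (0.70 + 0.65)/(1.75 + 0.65) = 1.31. When θ = 1 the expression is 1 throughout, so nothing is distorted under the null.

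**Step 2: the single Cox hazard ratio.** This is the value that solves the large-sample Cox score equation over Days 0 to 56. z is the expected Wald statistic. Restricted means only participants able to respond.

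| F₁ vs F₀ | π | HR restricted | HR all ITT | z restricted | z all ITT |
|---|---|---|---|---|---|
| 60% vs 15% | 20% | 5.64 | 5.13 | 6.17 | 5.85 |
| 60% vs 15% | 35% | 5.64 | 4.84 | 5.56 | 5.08 |
| 60% vs 15% | 45% | 5.64 | 4.67 | 5.12 | 4.57 |
| 80% vs 50% | 20% | 2.32 | 2.04 | 5.06 | 4.30 |
| 80% vs 50% | 35% | 2.32 | 1.91 | 4.56 | 3.52 |
| 80% vs 50% | 45% | 2.32 | 1.84 | 4.20 | 3.05 |

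The restricted hazard ratio is ln(1 − F₁)/ln(1 − F₀); for 60% vs 15% this is ln(0.40)/ln(0.85) = 5.64. In every row z is lower in all ITT than in the restricted set, despite the larger number of participants.

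**Step 3: a weaker effect.** With a hazard ratio of 1.5 and F₀ = 30%, the all-ITT value is 1.48 at π = 10% and 1.43 at π = 50%. Dilution is small when events are few.

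**Step 4: the median.** It is reached by Day 56 only if (1 − π) × F ≥ 50%. The response needed among those able to respond is 50%/(1 − π): 55.6%, 62.5%, 71.4%, 83.3% and 100% at π = 10%, 20%, 30%, 40% and 50%.

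- F₁ = 60%: 48%, 39% and 33% of all ITT have the event at π = 20%, 35% and 45%, so the expected curve never reaches a median. Restricted, the median is about Day 42.
- F₁ = 80%: 64%, 52% and 44%. The median moves from Day 24 (restricted) to Day 34, then Day 51, then is not reached.

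**Step 5: across thresholds.** Anyone below 2 is also below 3 and 4, so π cannot fall as k rises. The 4-point analysis is the most exposed.

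**The case against.** **Silence is not a decision to include.** Table 2.3.3 (4-point responders) is labelled ITT as well, and its entry in SAP 7.4.2.3 carries no limit, yet SAP 7.3.1.1 restricts it. A reader might infer from the ITT labels that the sponsor chose to keep low-itch participants in the time-to-event analyses; the labels do not show that. What stands is that no text restricts those analyses and the stated default is ITT. If a restriction is intended, it still has to be written.

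**The numbers rest on assumptions.** This is correct. The share below each threshold, the event rates and the hazard ratios are not in the documents. The event is the first qualifying single day, which is easier to meet than a weekly mean at Week 8, so 60% may be too low. A higher rate makes the median easier to reach but increases the dilution of the hazard ratio.

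**All-randomized is a legitimate target, and a median that is not reached is a valid result.** Also true. It answers a different question from the SAP's own 4-point proportion, and keeping it as a supportive analysis preserves it.

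**Restricting will not make the results match the key secondary endpoint.** This stands. That endpoint uses 7-day means with nonresponder imputation; time to response uses single daily scores. The restriction aligns the populations and nothing more.

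**SAP 7.3.1.1 supports the limit only for 4 points.** This is right. Limits of 2 and 3 extend its logic; the SAP does not contain them.

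**Conclusion.** The point holds as an avoidable weakness in secondary analyses. If followed as written and if the treatment works, the hazard ratio is pulled toward 1, the log-rank test loses power, and the planned median may not be reached. Under the assumed rates, 5.64 falls to between 5.1 and 4.7, and 2.32 to between 2.0 and 1.8, for 20% to 45% ineligible. The true size cannot be fixed from the documents.

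Three stronger readings are not supported:

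- **Risk of a false positive.** There is none from this source. Low-itch participants are balanced by randomization in expectation, and under no effect the hazard ratio stays at 1. Time to itch response is also outside the families in SAP 3.2.
- **Loss of a positive finding.** In the two illustrated scenarios z stays above 3. The main damage is to the estimates.
- **The median will be missing.** It may be, depending on the response rate and the ineligible share. It can also be missed in a restricted set if fewer than half respond.

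**What to change.** Add one sentence to SAP 7.4.1.2, and apply it in 7.4.2.3 and 7.4.2.4: each time-to-k-point analysis and each k-point responder table is run in ITT participants with baseline Itch NRS of at least k, for k = 2, 3 and 4. For k = 4 this repeats the rule in 7.3.1.1; for k = 2 and 3 it extends it. State that baseline means the 7-day average in 7.3.1.1, so that the restriction and the improvement use the same value. Keep the all-ITT version as supportive, relabel the affected tables and figures in Appendix A, and report the number excluded by arm.

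Baseline itch is measured before treatment starts, so the comparison stays randomized, and no new data are needed. The costs are fewer participants per analysis, although those removed cannot contribute an event, and slightly different (nested) populations for the three thresholds. The 2-, 3- and 4-point curves can then no longer be overlaid as one population; the supportive all-ITT version covers that use.
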